Title: Assessment of Urinary Neutrophil Gelatinase-Associated Lipocalin (NGAL) to Predict Acute Kidney Injury (AKI) in Children Receiving Multiple Nephrotoxic Medications (NINJA NGAL)

NCT03527160

Date: 13 November 2018

1. Background/Preliminary Studies

Nephrotoxic medication (NTMx) exposure is one of the most commonly cited causes of acute kidney injury (AKI) in hospitalized children¹, and is the primary cause of AKI in 16% of cases. Recent data from Texas Children's Hospital reveal more than 80% of non-critically ill children receive at least one NTMx (e.g., aminoglycosides, non-steroidal anti-inflammatory agents) during their hospitalization². NTMx-AKI is associated with increased hospital length of stay and associated health care costs; we found patients with NTMx-AKI secondary to intravenous aminoglycoside exposure spent a median of five additional days in hospital (additional cost of \$17,000) compared to children who were exposed but did not have AKI³. Furthermore, 10-49% of adults and children who survive an AKI episode develop chronic kidney disease⁴⁻⁷, which puts them at risk for hypertension and progression to kidney failure, requiring dialysis or a kidney transplant.

Through our initial work at Cincinnati Children's Medical Center, **we have found that NTMx exposure is potentially modifiable and the associated AKI is an avoidable adverse safety event**. In our single center systematic screening system to identify children at-risk for AKI called Nephrotoxic Injury Negated by Just in time Action (NINJA), we utilized an electronic health record trigger to improve near real-time clinical decision support collaboration between rounding physicians, pharmacists, nurses and patient families⁸. With this systematic screening, we found our baseline NTMx-AKI rates (2.96 per 1000 patient-days)⁸ were similar to published baseline central line blood stream⁹ and catheter associated urinary tract infection¹⁰ rates, suggesting that NTMx-AKI is as important as these US hospital acquired conditions which are national priorities. We recently published the 3½ year NINJA experience, demonstrating sustained decreases in NTMx exposures (38% reduction) and NTMx-AKI (68% reduction).¹¹ We calculated that CCHMC patients avoided more than 600 exposures and almost 400 NTMx-AKI episodes over that time period as a result of the NINJA program.

As a result of our single center success, we have been funded by the Agency for Healthcare Research and Quality to disseminate NINJA at nine other US pediatric hospitals. In the first 18 months of this project, we already observed a 30% reduction in NTMx-AKI rates. Four additional pediatric hospitals have joined the NINJA collaborative and have started to submit data. In aggregate, the Collaborative centers observe a monthly average of 200 patients with NTMx exposure leading to 35 NTMx-AKI episodes from 20,000 patient-days screened. In September 2016, NINJA was accepted as the next Hospital Acquired Condition (HAC) for the Solutions for Patient Safety (SPS); the SPS is a national harm reduction network of more than 100 pediatric institutions in the US and Canada funded by the Centers for Medicare and Medicaid Services. The HAC designation provides significant additional resources to disseminate NINJA to all SPS member hospitals starting in Winter 2017. Thus, the disseminated NINJA program provides a current unparalleled foundation and infrastructure for clinical-translational research to improve outcomes in children with, or at-risk for NTMx-AKI. With the integration of NINJA into SPS, the potential for clinical application of any diagnostic or therapeutic intervention to modify NTMx-AKI will expand exponentially.

While the NINJA quality improvement research related AKI reductions have been important, one in six children exposed to NTMx still develop AKI. In a pilot study assessing the ability of the novel AKI damage urine biomarker NGAL to predict AKI in a cohort of children with cystic fibrosis, we discovered that higher uNGAL levels predicted the AUC for the nephrotoxic medication tobramycin as well as predicting AKI.¹² Thus, we suggest that uNGAL may have a pivotal role in detecting AKI early as well as mitigating AKI with appropriate NTMx-dose adjustment. The proposed project will leverage the clinical infrastructure of NINJA to determine if NGAL could replace serum creatinine as the marker of choice in the epidemic of NTMx-AKI.

2. Rationale

Despite the success outlined above, one of the negative aspects of the NINJA program voiced by clinicians, nurses, families and patients stems from the pain and difficulty in obtaining daily blood samples on patients who meet high-NTMx exposure criteria. As most of the blood samples are performed in the early morning hours, blood draws not only cause pain, but can disrupt nighttime sleeping patterns and reduce patient satisfaction with medical care. In some programs, daily blood monitoring of high-risk patients is not performed limiting our ability to detect AKI and improve the ability of daily screening. Improving our ability to screen for NTMx-AKI with non-invasive urine biomarkers will make a tremendous impact in our ability to detect harm from NTMx medications and at the same time, reduce the difficulty and pain associated with daily blood draws.

In order to incorporate the use of urine NGAL into clinical practice we must first demonstrate that urine NGAL will not miss cases of serum creatinine based AKI (express a high sensitivity and a very low negative predictive value). If successful, we believe we can alter the approach to screening for NTMx-AKI as shown in the figure below. Our central hypothesis is that daily urine NGAL can replace daily serum creatinine measurements in children who meet criteria for high exposure risk according to standard NINJA criteria.

Hypothesis 1: Urine NGAL is highly sensitive to detect NTMx-associated AKI

A. Methods - We will continue to measure serum creatinine values daily according to current NINJA protocol. A once daily urine sample will be obtained for 7 days from each participant who meets the high nephrotoxic medication exposure criteria (receiving 3 or more NTMx on the same day, or 3 or more days of an intravenous aminoglycoside). We will collect urine using a urine bag, or collected as a natural void. Urine will be processed, frozen and banked for future testing. Urine NGAL will be measured in batch in the CCHMC Clinical Lab which has the NGAL assay on their platform. These results will not be posted in EMR.

Hypothesis 2: Bedside testing of urine from high risk NTMx-exposed participants are adequate and reliable compared to uNGAL measured from the clinical platform.

A. Methods - using the urine collected above, we will evaluate urine NGAL using the Bioporto bedside POC test at the time of urine collection. The POC assay is a

colorimetric assay and a “low-risk” reading correlates with the clinical lab based NGAL reading of < 50 ng/ml.

3. Study Design:

This study is a multicenter prospective observational study.

Using the Electronic Medical Record (EMR) generated report, at-risk patients will be identified which is part of our standard of care. At-risk patients are defined as patients meeting high-NTMx exposure criteria. Once identified as a potential research participant one of the research investigators will then contact the primary medical team to ask their permission to approach the participant and family. Once the research team has approval to approach the participant and family, one of the research study coordinator’s will then approach the participant/participant’s family regarding potential enrollment and to obtain informed consent and assent as indicated. Once informed consent is given, a detailed medical record review will be performed on these participants; which may include demographic information, medical history, medications, laboratory values, vital signs, and urinary biomarkers. Data from medical records will be abstracted into an electronic research database. Data collection sheets will be identified by a unique study identification number not based on PHI. A key linking participant names and medical record numbers to study identification numbers will be stored on a password-protected computer, separate from the study data, by the principal investigator or his designee.

3A. Bone Marrow Transplant Repository

Urine samples will be obtained from the Bone Marrow Transplant Repository who meet the NINJA criteria of 3 or more NTMx in a day or IV aminoglycosides given for three or more consecutive days. For those participants enrolled in the BMT Repository that meet NINJA criteria, once daily urine samples will be obtained from the Repository.

4. Consent/HIPPA Authorization

Non-BMT Participants: We plan to obtain informed consent from parents and directly from of-age participants if applicable- as well as assent from participants over the age of 11- to participate in the study at the time of NTMx exposure. Before enrollment, permission from the attending physician caring for the participant will be obtained. After permission is granted from the attending physician, consent will be obtained from the parents, legal guardian, or legally authorized representative in their primary language. An interpreter will be provided if necessary. A short form consent in Spanish will be available for Spanish speaking subjects. If a subject speaks a language other than English or Spanish, a short form consent in their native language will be submitted to the IRB and approved prior to enrollment. Because standard safeguards will be employed to protect PHI, this study represents no more than minimal risk to participants. The consent process and HIPAA authorization will not adversely affect the rights or welfare of participants.

BMT Participants: Justification of Waiver of Consent & HIPAA Authorization: We are requesting a waiver of the informed consent process and requirement to obtain HIPAA authorization from participants enrolled in the BMT repository at CCHMC. Use of their urine for NGAL involves the review of information that is already in existence at the time this research is being submitted and study staff will not have any direct contact with the research participants enrolled in the BMT repository. We believe the request for a waiver of consent and HIPAA authorization from BMT participants who have consented to provide urine to the BMT repository meets the necessary criteria for a waiver of consent and HIPAA authorization per 45CFR46.116(d) as follows:

- a. The use or disclosure of Protected Health Information (PHI) represents no more than minimal risk because:
 - i. An adequate plan exists to protect the identifiers from improper use and disclosure. See “Potential risks, discomforts, and inconveniences: Mechanism proposed to minimize the participant’s potential risks involving confidentiality” and “Security.”
 - ii. There are adequate written assurances that the PHI will not be reused or disclosed to any other person or entity, except as required by law, for authorized oversight of the research study, or for other research for which the use or disclosure of PHI would be permitted. See “Security.”
- b. The research could not practically be conducted without the access to and use of the PHI. Critically ill patients receiving care from BMT are eligible for multiple studies, both interventional and observational. This patient population is also understandably under a great deal of stress and the BMT repository has been created to minimize multiple requests for study participation, specifically those involving collection of samples collected by non-invasive means, such as urine.

5. Statistical Analysis Plan: We plan to enroll at least 100 subjects, 30 of whom will need to develop AKI by the KDIGO serum creatinine criteria (50% rise over baseline or a 0.3 mg/dl rise over baseline within 48 hours). If we have not enrolled at least 30 participants with AKI after a 100 participant total enrollment, we will continue to enroll up to another 100 participants to achieve a total of 30 AKI participants. Our current data from the NINJA project show that 15% of exposed participants develop AKI. For hypothesis 1, we will determine the sensitivity, specificity, positive predictive value and negative predictive value of urine NGAL to detect NTMx-AKI. Our goal is to achieve a NPV of >98% using an uNGAL concentration of <50 ng/ml to rule out serum creatinine based AKI development. For hypothesis 2, we will also assess sensitivity, specificity, PPV and NPV for the POC “low-risk” test to predict a clinical lab based NGAL level of <50 ng/ml.

Sample size estimates: With an assumption that 70 participants will not develop AKI in the first 7 days, we will have 490 samples for comparative analysis if we are able to stop at 100

participants. If we need to enroll 200 participants to achieve enroll 30 AKI participants, we would have 1190 samples (170x 7 days) for participants without AKI. Sample size analysis for non-inferiority (of NGAL to serum creatinine, of POC NGAL to clinical lab NGAL) reveals that we need 143 samples to be confident that we will not see a >2% discordance rate between the reference and test data set with a power of 0.8 and an alpha of 0.05. Clearly, we will have enough samples in the dataset. If we analyze the data on a per participant basis, again we will have enough participants if we enroll 200 total. At the minimum of 100 participants, our power is 0.67.

6. Security

Participant confidentiality will be maintained throughout the study, through the use of a numeric coding system. Data will be stored using a secure EDC system (REDCap) and access will be limited to study staff.

The records from this study will be kept confidential to the extent allowed by law. Representatives of Cincinnati Children's Hospital Medical Center ("CCHMC"), the Investigator and CCHMC employees involved with the research study including the Institutional Review Board and the Office for Research Compliance and Regulatory Affairs, and any sponsoring company or their appointed agent as well as National Institutes of Health / National Institute of Child Health and Human Development, and the United States Food and Drug Administration may also be allowed to inspect the medical and research records related to this study. If the results of this study are published, no Protected Health Information (PHI) will be disclosed, and subjects will not be identified by name. Research data will be stored in a secure location, with limited access.

7. Future Use

The data obtained from sites will be saved according to HIPPA guidelines and will be maintained in a de-identified format in REDCap. No PHI will be used for future research without prior IRB approval. Urine samples will be maintained for a minimum of five years and will not be used for future research without prior IRB approval.

Figure 1: Current Screening for NTMx-AKI

[figure not shown]

Figure 2: Screening for NTMx-AKI during study

[figure not shown]
[figure not shown]

Figure 3: Goal for screening if we can validate hypothesis

References

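### Does a cap of 200 participants put the plan's 30 AKI cases out of dependable reach?

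*Combined protocol and SAP*

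**What the plan says.** Section 5 (Statistical Analysis Plan) sets a minimum of 100 subjects, "30 of whom will need to develop AKI by the KDIGO serum creatinine criteria". If 30 have not been found by then, "we will continue to enroll up to another 100 participants to achieve a total of 30 AKI participants", which makes 200 the ceiling. The supporting rate is given directly afterwards: "Our current data from the NINJA project show that 15% of exposed participants develop AKI".

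The sample-size paragraph works through two end points. With 70 AKI-free participants over 7 days, "we will have 490 samples for comparative analysis if we are able to stop at 100" participants. If 200 are needed to obtain 30 cases, "we would have 1190 samples (170x 7 days) for participants without AKI". Both totals are compared with a requirement of 143 samples at power 0.8 and alpha 0.05. For the alternative unit of analysis it says "If we analyze the data on a per participant basis, again we will have enough participants if we enroll 200 total", and then "At the minimum of 100 participants, our power is 0.67".

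Section 1 (Background/Preliminary Studies) gives two further rates: one in six exposed children, and 35 AKI episodes per 200 exposed patients per month.

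**The concern.** The 30 cases are worded as a need, but enrolment stops at the number that supplies them only on average. A design sized to an expected count misses it almost half the time. The plan does not state that risk, and it does not say how the study would be reported if it closed at 200 with fewer than 30.

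The 100-participant scenario raises a related doubt. Finding 30 cases in 100 needs a rate of about 30%, twice the cited figure, yet the 490-sample total and the 0.67 power are given for that size without comment.

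AKI participants are the denominator of per-participant sensitivity, and Hypothesis 1 is that urine NGAL is highly sensitive. Too few cases would make that estimate less precise.

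**Working it through.** **Inputs.** From Section 5: target 30, first stage 100, cap 200, AKI rate 15%, 7 daily samples, requirement 143 samples. From Section 1: one in six (16.7%), and 35/200 (17.5%, which counts episodes and so may overstate the per-participant rate).

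**The plan's own figures.**
- 200 × 0.15 = 30, equivalently 30/0.15 = 200. The plan does not say that the cap was derived this way.
- 70 × 7 = 490 and 170 × 7 = 1190.
- Power at 100: scale from 143 samples at power 0.80 with one-sided alpha 0.05 (normal approximation; the plan does not state sidedness). (1.645 + 0.842)/√143 = 0.208, and Φ(0.208 × √100 − 1.645) = 0.668, which matches 0.67. The scaling uses total numbers only and contains no AKI count.

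**Chance of reaching 30.** With X ~ Binomial(n, p), P(X ≥ 30) is as follows. Stopping early at 30 cases does not change the 200-participant column.

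| AKI rate | Expected count at 200 | P(≥30 by 200) | P(≥30 by 100) |
|---|---|---|---|
| 15% | 30.0 | 53.0% | 0.01% |
| 16.7% | 33.3 | 76.3% | 0.07% |
| 17.5% | 35.0 | 84.7% | 0.15% |

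An 80% chance by 200 needs a rate of 17.0%. An even chance of stopping at 100 needs 29.6%.

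**Size of a shortfall.** Given fewer than 30 at 200, the mean count is 25.7, 26.6 and 26.9 at the three rates. At 15%, the chance of at least 25 cases is 86%, and the 5th percentile is 22.

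**Effect on sensitivity.** With no missed cases, the exact two-sided 95% lower limit is 0.025^(1/n):
- n = 30: 88.4%
- n = 27: 87.2% (loss 1.2 points)
- n = 26: 86.8% (loss 1.7 points)
- n = 22: 84.6% (loss just under 4 points)

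**Effect on sample totals.** Expected enrolment under the stopping rule is 100 + Σ P(X_n ≤ 29) over n = 100 to 199, which gives 187, 175 and 169. Multiplying the unrounded values by (1 − p) × 7 gives about 1110, 1020 and 970 AKI-free samples. A close at 200 with 26 cases gives 174 × 7 = 1218. All are far above 143.

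**The case for a change.** The best case for acting is that the edit is cheap and honest. Rewording 30 as a target, stating the chance of meeting it and labelling the 100-participant case would take a few sentences and no added enrolment. A final count of 26 would then look foreseen and not like a failure. Saying that enrolment may go up to a ceiling does not tell the reader that, at the cited rate, missing the target is nearly as likely as meeting it. Clustering across centres would lower the odds further: with an assumed intraclass correlation of 0.005 to 0.02 (beta-binomial; not from the documents), the three chances by 200 become about 48–51%, 60–68% and 65–76%.

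The arithmetic in this argument stands, and so does the observation that the plan prints no probability. The inference that a reader is misled is weaker. Each scenario is introduced conditionally, the ceiling is explicit, and the 15% rate stands beside it, so the multiplication is there for any reader to do.

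A printed probability would also suggest more certainty than the inputs allow. Section 2 notes that in some programs "daily blood monitoring of high-risk patients is not performed limiting our ability to detect AKI", so the cited rates may be low. The 7-day window could act the other way. No rate is given for the bone marrow transplant repository participants admitted under Section 3A. The very small chances of stopping at 100 are especially sensitive: under the same assumed clustering they rise to 0.2–1.9% at 15%. Very unlikely is a fair description, and a more exact figure is not supported.

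**Conclusion.** No change follows. The plan contains no wrong figure and never calls 30 cases assured. It sets a case target, a ceiling on effort and a planning rate, and at that rate the target is about an even bet (53%, assuming independent participants with one common rate). Accepting that in return for a bounded enrolment is a fair trade-off in an observational study.

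Little depends on the exact count. The sample requirement and the stated power are expressed in samples or total participants, and the NPV goal is not tied to 30 cases. Section 5 already rests its per-participant claim on 200 enrolled, so the 100-participant case is a boundary and not the basis of the design. If the study closes at 200 with 26 cases, the analysts would report the same accuracy measures on the cases they have, and the count would show the precision. The typical loss of 1.2 to 1.7 points assumes a per-participant analysis, an exact interval and no missed cases, none of which the plan commits to. The missing probability is detail that any reader can supply, and adding it would not improve the study's conduct or its conclusions.

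### The NPV goal of more than 98% has no confidence bound or test and is not tied to the 2% discordance used to size the study

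*Combined protocol and SAP*

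**What the plan says.** All of this is in Section 5 (Statistical Analysis Plan) unless noted.

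- **Target for hypothesis 1:** "Our goal is to achieve a NPV of >98% using an uNGAL concentration of <50 ng/ml".
- **Planned analysis:** "we will determine the sensitivity, specificity, positive predictive value and negative predictive value of urine NGAL to detect NTMx-AKI". No interval, bound, null hypothesis or success rule follows.
- **Sizing:** the calculation is framed as non-inferiority, both for uNGAL against creatinine and for the bedside test against the laboratory assay. Its result is that "we need 143 samples to be confident that we will not see a >2% discordance rate between the reference and test data set". Power is set at 0.8 and alpha at 0.05. The assumed true discordance and the sidedness of alpha are not given.
- **Unit of analysis:** samples come first (490 from 70 children without AKI, or 1190 from 170). A per-participant analysis is mentioned as a possibility, for which "At the minimum of 100 participants, our power is 0.67".
- **Purpose (Section 2, Rationale):** the study must show that uNGAL does not miss creatinine-based AKI before it can take over from daily creatinine. That sentence asks that uNGAL "express a high sensitivity and a very low negative predictive value", which is the reverse of the goal in Section 5.

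**The concern.** The sizing speaks of confidence at a stated alpha; the analysis speaks only of determining accuracy measures and reaching a goal. Nothing connects the two. A reader of the final report could therefore see an observed NPV a little above 98% and take it that a miss rate above 2% has been excluded, when the plan contains no step that would establish this.

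NPV is the only accuracy measure with a numerical target, and it supports the case for dropping daily creatinine. With roughly 40 to 170 NGAL-negative children, the observed NPV moves in steps of about 0.6 to 2.4 percentage points per missed case (1/170 to 1/42), so whether it lies above 98% depends on one, two or three children. If the way of judging it is left open, the choice between point estimate and bound can be made after the data are seen.

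**Working it through.** **1. The plan's own figures.** Scaling from 143 samples at power 0.80 and one-sided alpha 0.05, power at 100 is Φ((1.645 + 0.842) × √(100/143) − 1.645) = 0.668, which matches the stated 0.67. The figure of 143 itself could not be reproduced. A non-inferiority comparison of two proportions with a 2-point margin and one-sided alpha 0.05 gives 606, 307 or 154 for proportions of 98%, 99% or 99.5%. The zero-failure bound ln(0.05)/ln(0.98) = 148.3 gives 149. This is not shown to be an error, since the assumed discordance is not stated. It does mean that 143 cannot be traced to a test of NPV.

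**2. Inputs.** Children without AKI: 70 (at 100 enrolled) or 170 (at 200 enrolled), from Section 5. Specificity is not stated; 60%, 80% and 100% are assumed. NGAL-negatives n ≈ children without AKI × specificity. This ignores the few missed cases, which are also NGAL-negative; the effect is small.

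**3. Chance of meeting the goal on the point estimate.** With n negatives, observed NPV > 98% requires at most c misses, where c is the largest whole number with (n − c)/n > 0.98. The chance is P(X ≤ c), X ~ Binomial(n, 1 − true NPV).

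Example, n = 136: 134/136 = 98.5% passes and 133/136 = 97.8% does not, so c = 2. At true NPV 97%: 0.97^136 + 136 × 0.03 × 0.97^135 + 9180 × 0.03² × 0.97^134 = 0.016 + 0.067 + 0.139 = 0.222.

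| Enrolled | Specificity (assumed) | n | c | True NPV 98% | 97% | 96% | One-sided 95% lower bound at c misses |
|---|---|---|---|---|---|---|---|
| 100 | 60% | 42 | 0 | 0.43 | 0.28 | 0.18 | 93.1% |
| 100 | 80% | 56 | 1 | 0.69 | 0.50 | 0.34 | 91.8% |
| 100 | 100% | 70 | 1 | 0.59 | 0.38 | 0.23 | 93.4% |
| 200 | 60% | 102 | 2 | 0.67 | 0.41 | 0.22 | 94.0% |
| 200 | 80% | 136 | 2 | 0.49 | 0.22 | 0.09 | 95.4% |
| 200 | 100% | 170 | 3 | 0.56 | 0.25 | 0.09 | 95.5% |

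Because c moves in whole steps, the chance jumps between these rows. Over every n from 42 to 70, the figure at true NPV 97% runs from 22% (n = 50) to 55% (n = 51). Over every n from 102 to 170 it runs from 17% (n = 150) to 41% (n = 102). All exceed 5%.

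**4. Per sample.** If all 490 samples were negative and independent (c = 9), the chance at true NPV 97% is 0.077. With 1190 (c = 23) it is 0.015. At true NPV 98% both are still close to one half (0.48 and 0.49). Up to seven daily samples from the same child are correlated, so the effective number is smaller and these figures are optimistic.

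**5. What a bound can deliver.** With no misses, the exact one-sided 95% lower bound is 0.05^(1/n). This gives 97.996% at n = 148 and 98.010% at n = 149, so 149 negatives without a miss is the minimum for a bound above 98%. At 100 enrolled, 70 negatives give at best 95.8%. At 200 enrolled, 149 of 170 requires a specificity of at least 149/170 = 87.6%. With all 170 negative, no misses gives 98.25%, and this is the only result that passes. Its probability is 0.99^170 = 0.18 at true NPV 99% and 0.995^170 = 0.43 at 99.5%.

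**The case against.** The stronger reading, that the plan judges NPV on a point estimate and would declare success for a test whose true NPV is below 98%, is tempting but not supported. Section 5 never says that the observed value decides. It calls 98% a goal and defines no declaration of success, and the phrase about being confident, with its alpha, could be read as an intended bound. This objection stands: the gap is an unstated rule, not a wrong one, and the probabilities above hold only if the point estimate is used.

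A reader might also treat the 2% as the permitted miss rate among NGAL-negatives. The plan refers to a "discordance rate between the reference and test data set" and does not define it further; it could include false positives. The match between 2% and 98% is suggestive but not a documented link, so the bounds here are set against the 98% goal and not against the sizing margin.

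The per-sample figures are much lower than the per-participant ones, and the plan puts samples first. That is a fair point and is why both are shown. It does not remove the concern, because independence is implausible and the unit is left open.

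A pass rate near one half at a true NPV of exactly 98% is what any point-estimate rule gives, and is no separate fault. Finally, the reversed wording on NPV in the Rationale is a slip. The same sentence says that cases must not be missed, so it misleads nobody about intent and adds nothing to the statistical argument.

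**Conclusion.** The point holds as a gap in specification with a measurable consequence. Section 5 sets an NPV goal without a bound or test and does not relate it to the non-inferiority sizing, so the confidence invoked in the sizing is not delivered by any planned analysis of NPV. If the observed NPV is compared with 98%, a true NPV of 97% meets the goal about 22-41% of the time per participant at 200 enrolled (102, 136 or 170 negatives) and about 28-50% at 100 enrolled (42, 56 or 70 negatives). Per sample it is 8% or 1.5% under all-negative, independent sampling, which understates the risk.

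These figures rest on assumed specificities of 60-100%, on the plan's counts of 70 or 170 children without AKI, and on a binomial model with one result per child. The point should be dealt with before analysis. It is not fatal, because the counts collected will allow a bound to be calculated.

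**What to change.** Keep NPV above 98% as the target, and add to Section 5 wording to this effect:

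- Participant-level NPV is reported with an exact (Clopper-Pearson) one-sided 95% lower bound. The plan states how a child with several daily samples is classed as NGAL-negative.
- Any sample-level NPV is reported with a lower bound that allows for clustering by participant.
- The rule-out claim is limited to the bound reached. A miss rate above 2% is said to be excluded only if the lower bound for NPV exceeds 98%.
- Discordance in the sample-size paragraph is defined, with its assumed true rate and the sidedness of alpha, and its relation to NPV is stated.

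The cost is some SAP wording and one further calculation, plus a downside that should be stated openly. Per participant, a bound above 98% is out of reach at 100 enrolled. At 200 it is reachable only with high specificity and no misses. The headline will therefore usually be weaker than an NPV above 98%; three misses in 170, for example, would support a claim of about 95.5%. Making the bound a pass/fail rule with 80% power would need about 386 independent negatives at a true NPV of 99.5%, or about 969 at 99%. No such extra enrolment is proposed.

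Separately, as a clerical correction, the Rationale should ask for a very high, not a very low, negative predictive value.

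### The sample-size assurance for NGAL against creatinine rests on samples from children without AKI, so it does not support the sensitivity aim of Hypothesis 1

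*Combined protocol and SAP*

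**What the plan says.** Section 2 (Rationale) makes it a condition of clinical use that NGAL should not overlook creatinine-defined AKI, and Hypothesis 1 is a claim of high sensitivity. For that hypothesis, section 5 lists sensitivity, specificity, PPV and NPV as outputs and sets one numerical target: "Our goal is to achieve a NPV of >98% using an uNGAL concentration of <50 ng/ml". At least 100 children are to be enrolled and 30 AKI cases are sought, with up to 100 more children if needed. On the expected rate: "Our current data from the NINJA project show that 15% of exposed participants develop AKI".

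The sample-size paragraph then counts samples. For a stop at 100 participants: "With an assumption that 70 participants will not develop AKI in the first 7 days, we will have 490 samples for comparative analysis". For 200: "we would have 1190 samples (170x 7 days) for participants without AKI". The requirement is introduced as "Sample size analysis for non-inferiority (of NGAL to serum creatinine, of POC NGAL to clinical lab NGAL") and given as 143 samples to rule out discordance above 2%, with power 0.8 and alpha 0.05. The conclusion is "Clearly, we will have enough samples in the dataset". For a participant-level analysis the plan adds "If we analyze the data on a per participant basis, again we will have enough participants if we enroll 200 total" and "At the minimum of 100 participants, our power is 0.67".

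The plan gives no assumed sensitivity, no interval or power for sensitivity or NPV, and no reason for choosing 30 AKI cases.

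**The concern.** Sensitivity is estimated from children who develop AKI. The samples counted to show adequacy exclude all of them. In a set of samples that are all AKI-negative, NGAL can disagree with creatinine only by a false positive. A missed AKI cannot occur there.

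The participant-level statement may include the AKI children, but it is power for discordance. The plan does not say whether that means missed AKI among NGAL-negatives or every disagreement in either direction.

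The intended use is to replace daily creatinine in high-risk children, so a false negative is the error that matters most. A reader could take the adequacy statement as covering that error, when about 30 AKI cases can address it only with wide uncertainty.

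**Working it through.** **Inputs.** From section 5: 70 or 170 children without AKI, a target of 30 with AKI, totals of 100 or 200, AKI rate 15%, 143 samples at power 0.8 and alpha 0.05, a 2% discordance limit, and the NPV goal. From section 2: one urine sample a day for 7 days. From section 1: AKI in one in six exposed children, and 35 episodes per 200 exposed patients. Sidedness, specificity and one NGAL result per child are my assumptions.

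**1. The plan's own figures.** 70 × 7 = 490 and 170 × 7 = 1190, as stated. Taking 143 as given, power at n is Φ[(z₁₋α + z₀.₈₀)√(n/143) − z₁₋α]. At n = 100 with one-sided alpha 0.05 this is Φ[(1.645 + 0.842) × 0.836 − 1.645] = 0.668, which matches the stated 0.67. With z = 1.960 it is 0.649. At n = 70 (one-sided) it is 0.54, so the 0.67 appears to count all 100 children. The 143 itself cannot be rebuilt, because the expected discordance rate is not given.

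**2. What 2% discordance would imply for misses.** If discordance means all disagreements, and a true rate of 2% consisted only of misses, sensitivity would be 1 − 0.02N/30:

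- N = 200: 1 − 4/30 = 86.7%
- N = 100: 1 − 2/30 = 93.3%

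These are bounds that correspond to a true rate of 2%. They are not observed counts that the plan would accept.

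**3. Precision for sensitivity.** Exact (Clopper-Pearson) two-sided 95% lower limits follow. With no misses the limit is 0.025^(1/n).

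| Detected / AKI cases | Sensitivity | Lower limit |
|---|---|---|
| 30/30 | 100% | 88.4% |
| 29/30 | 96.7% | 82.8% |
| 28/30 | 93.3% | 77.9% |
| 27/30 | 90.0% | 73.5% |
| 25/25 | 100% | 86.3% |
| 20/20 | 100% | 83.2% |

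The one-sided 95% limit for 30/30 is 90.5%.

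**4. Chance of reaching 30 cases.** With X binomial(200, p), P(X ≥ 30) is 0.53 at p = 0.15. It is 0.76 at one in six, and 0.85 at 35/200 if each episode is a different patient. Among 100 children at 15% it is about 0.0001.

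**5. What the NPV goal requires.** NPV = t/(t + m), with t true negatives and m missed cases. For NPV above 98% with 30 AKI cases:

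- N = 200 (170 non-AKI): m = 3 needs t ≥ 148, since 148/151 = 98.01% while 147/150 = 98.0% is not above the goal. That is 148/170 = 87% testing negative, with sensitivity 27/30 = 90.0%. At best, 170/173 = 98.3%, lower limit 95.0%. m = 4 always fails (170/174 = 97.7%).
- N = 200 with an assumed specificity of 70% (t = 119): m = 2 passes (119/121 = 98.3%, lower limit 94.2%) and m = 3 fails (119/122 = 97.5%).
- N = 100 (70 non-AKI): m = 1 needs t ≥ 50 (50/51 = 98.04%), and m = 2 always fails (70/72 = 97.2%). Observed sensitivity must then be at least 29/30 = 96.7%.

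With no misses and perfect specificity, the NPV lower limits are 94.9% (70/70) and 97.9% (170/170).

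**The case against.** The strongest reply is that misses are a subset of all disagreements, so a limit on total discordance also limits misses, and false positives only make the test harder to pass. The implied floors of 86.7% and 93.3% are not far from the 88.4% that 30/30 would give. The imprecision therefore comes from having 30 cases, not from the criterion. This stands for a participant-level analysis that includes the AKI children. It does not rescue the sample counts of 490 and 1190, which contain none.

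A second reply is that 2% is exactly 1 − 98%, so the 143 may be an NPV calculation. With no misses, 149 NGAL-negatives would put a one-sided exact 95% limit above 98% (0.05^(1/149) > 0.98), close to 143. This reading is open because discordance is undefined. A reader might infer that the 2% criterion is certainly overall disagreement, or that it belongs only to Hypothesis 2. The documents establish neither.

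A reader might also infer that the plan would accept 4 discordant children of 200, or 2 of 100. It would not: the aim is to exclude 2%, and those counts have one-sided 95% upper limits of 4.5% and 6.2%.

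Finally, the plan does attend to AKI numbers. It seeks 30 cases, extends enrolment to find them, names sensitivity as an output and discloses the 0.67. The study is observational, NGAL results stay out of the medical record, and intervals could be added at reporting. All of this is true, but none of it supplies a precision for sensitivity or corrects the assurance already written.

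**Conclusion.** The point holds. The statement that there are clearly enough samples is an adequacy claim that the design does not have for sensitivity. The best available two-sided lower limit is 88.4% with 30 AKI cases and 83.2% with 20, and at the plan's own rate 30 cases is little better than an even chance. The NPV goal does not close the gap at 200 participants: it can be met at 90.0% sensitivity, though only with specificity of at least 87%.

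These figures assume one NGAL result per child, independent children and exact intervals. The plan gives no rule for reducing up to seven daily values to one result. That is a separate omission and not part of this point.

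Three stronger readings are not supported. The 143 is not shown to be wrong; an input is missing. The study is not shown to be unable to address Hypothesis 1; it can estimate sensitivity, with wide intervals. The plan does not ask for an NPV lower limit above 98%, so failing to reach one would not breach its goal.

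**What to change.** For Hypothesis 1, withdraw the sample-count assurance as support for sensitivity. Replace it with per-participant precision under one named interval convention:

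- Sensitivity from the AKI children, at 20, 25 and 30 cases.
- NPV from the NGAL-negative children, at 100 and 200 participants over a range of specificity.

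State that NPV above 98% is a point-estimate goal, and limit the rule-out conclusion to what the intervals support.

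Keep the 143 calculation only if discordance is defined, either as missed AKI among NGAL-negatives or as all disagreements, with its denominator, expected rate and sidedness stated. Then compare it with the matching count: NGAL-negatives for the first definition, all units analysed for the second.

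The cost is SAP wording and a short table. The stated assurance becomes less favourable. No extra patients or procedures are needed.
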